7.1. Screening and Enrollment Visit

Table 1: Screening and Enrollment Visit

Screening and Enrollment Visit	
Component	Procedure/Analysis
Administrative: Screening	Informed Consent Review Parent Study Records to Confirm HIV-1 Seroconversion Eligibility Determination
Administrative: Enrollment	Assign Participant ID Update Locator Information Update Demographics Schedule Next Visit Reimbursement
Clinical	Update Medical History Record Clinical Events Acute Seroconversion Assessment Concomitant Medications Assessment *Antiretroviral Treatment Record Complete Physical Exam (See Appendix IV) Gynecologic Exam (See Appendix IV) *Provide Test Results *Treatment or Referral
Behavioral	Baseline Behavioral Questionnaire *Adherence Questionnaire STI Risk Reduction and Contraception Counseling HIV Secondary Prevention Counseling Provision of Condoms
Urine	Qualitative hCG SDA for Chlamydia and Gonorrhea
Blood	Complete Blood Count Liver and Renal Function Tests Syphilis Serology CD4+ T-Cell Count Plasma HIV-1 RNA HIV-1 Genotypic Resistance Test (MTN NL, archived plasma) HSV-2 Antibody (site lab, regional lab, or MTN NL, archived plasma) HIV ELISA and Western Blot (MTN NL, archived serum)**
Pelvic Samples	Vaginal pH Wet Mount for bacterial vaginosis (BV), Candida, and Trichomonas †Pap Smear at Selected Sites
Specimens for Storage	Vaginal Swabs Cervicovaginal Lavage Plasma Serum Peripheral Blood Mononuclear Cells (PBMC)

*If indicated, **If not previously confirmed in a Network Laboratory, † PAP smears should be done at 6 month intervals in the first year after seroconversion, and then annually if the initial tests are negative.

7.2. Follow-up Visits

This study utilizes two follow-up visit schedules, one based on the date of identification of seroconversion in the parent study and one based on initiation of ART use.

- Participants who have not initiated use of ART at the time of enrollment in MTN-015 will follow the schedule based on the date of identification of seroconversion, which is described in Section 7.2.1. On this schedule, follow-up visits occur at Months 1, 3, and 6 after the date of identification of seroconversion, and every 6 months thereafter. Participants may enroll anytime after seroconversion. Following the enrollment visit, the subsequent visits will be scheduled according to the seroconversion date (for example, a participant who enrolls 4 months after seroconversion would have a second visit at 6 months after seroconversion (2 months after enrollment) and then every 6 months).
- Participants who have initiated use of ART at the time of enrollment in MTN-015 will follow the schedule based on the date of ART initiation, which is described in Section 7.2.2. On this schedule, follow-up visits occur at Week 2 and Months 1, 3, and 6 after the date of ART initiation, and every 6 months thereafter.
- Participants who initiate use of ART during follow-up in MTN-015 will follow the schedule in section 7.2.1, and then switch to the schedule in Section 7.2.2 after initiation of ART use.

As it will not always be possible to conduct follow-up visits on the target dates specified above, visits may be completed at any time during allowable visit windows. For both the non-ART and ART visit schedules, the allowable visit windows are contiguous and extend from the midpoint of one visit interval to the midpoint of the next visit interval. For example, the Month 24 visit window extends from Month 21 through Month 27. For participants who do not complete scheduled visits within the allowable window, the visit will be considered missed and relevant case report forms will be completed to document the missed visit. Missed visits will not be considered protocol violations.

7.2.1. Visits for non-ART Participants

Tables 2 and 3 list procedures that will be conducted for participants who have not initiated use of ART prior to these visits. For participants who have initiated ART prior to these visits, procedures specified in Tables 4 and 5 will be followed.

Table 2: Month 1 and Month 3 Post-Seroconversion Visits

Month 1 and Month 3 Post-Seroconversion Visits	
Component	Procedure/Analysis
Administrative	Update Locator Information Schedule Next Visit Reimbursement
Clinical	Update Medical History Update Clinical Events Concomitant Medications Assessment Targeted Physical Exam Gynecologic Exam *Provide Test Results *Treatment or Referral
Behavioral	Follow-up Behavioral Questionnaire (at Month 3 Post-Seroconversion Only) Social Harms Assessment (at Month 3 Post-Seroconversion Only) Provision of Condoms
Urine	*Qualitative hCG *SDA for Chlamydia and Gonorrhea
Blood	Plasma HIV-1 RNA CD4+ T-Cell Count *Syphilis Serology Complete Blood Count (at Month 3 Post-Seroconversion Only) Liver and Renal Function (at Month 3 Post-Seroconversion Only)
Pelvic Samples	*Vaginal pH *Wet Mount for BV, Candida, and Trichomonas */ [†] Pap Smear at Selected Sites
Specimens for Storage	Vaginal Swabs Cervicovaginal Lavage Plasma PBMC

*If indicated; [†]PAP smears should be done at 6 month intervals in the first year after seroconversion, and then annually if the initial tests are negative.

Table 3: Month 6 and Q6 Months Post-Seroconversion Visits

Month 6 and Q6 Months Post-Seroconversion Visits	
Component	Procedure/Analysis
Administrative	Update Locator Information Schedule Next Visit Reimbursement
Clinical	Update Medical History Update Clinical Events Concomitant Medications Assessment Targeted Physical Exam Gynecologic Exam *Provide Test Results *Treatment or Referral
Behavioral	Follow-up Behavioral Questionnaire (Month 12 and Month 24 only) Social Harms Assessment STI Risk Reduction and Contraception Counseling HIV-1 Secondary Prevention Counseling Provision of Condoms
Urine	*Qualitative hCG **SDA for Chlamydia and Gonorrhea (annually)
Blood	Plasma HIV-1 RNA CD4+ T-Cell Count Complete Blood Count Liver and Renal Function **Syphilis Serology (annually)
Pelvic Samples	**Vaginal pH **Wet Mount for BV, Candida and Trichomonas † Pap Smear at Selected Sites (annually)
Specimens for Storage	Vaginal Swabs Cervicovaginal Lavage Plasma PBMC

*If indicated; **Urine SDA for Chlamydia and Gonorrhea, Syphilis Serology, Vaginal pH, and Wet Mount should be performed at visits annually, with performance of these measures at additional scheduled visits as clinically indicated; †PAP smears should be done at 6 month intervals in the first year after seroconversion, and then annually if the initial tests are negative.

7.2.2. Follow-Up Visits for Participants after ART Initiation

Tables 4 and 5 below list procedures that will be conducted for participants who enroll after initiation of ART or who initiate ART during follow-up in MTN-015.

Table 4: Week 2, Month 1, and Month 3 After Initiation of ART

Week 2, Month 1, and Month 3 After Initiation of ART	
Component	Procedure/Analysis
Administrative	Update Locator Information Schedule Next Visit Reimbursement
Clinical	Update Medical History Update Clinical Events Concomitant Medications Assessment Antiretroviral Treatment Record Targeted Physical Exam Gynecologic Exam *Provide Test Results *Treatment or Referral
Behavioral	Follow-up Behavioral Questionnaire (Month 3 only) If ART is begun more than 24 months after identification of seroconversion, then the Follow-up Behavioral Questionnaire is omitted at post-ART visits. Adherence Questionnaire (Month 3 only) Social Harms Assessment Provision of Condoms
Urine	*Qualitative hCG *SDA for Chlamydia and Gonorrhea
Blood	Plasma HIV-1 RNA CD4+ T-Cell Count *Syphilis Serology *Complete Blood Count *Liver and Renal Function Tests *HIV-1 Genotypic Resistance Test (at NL)
Pelvic Samples	*Vaginal pH *Wet Mount for BV, Candida, and Trichomonas */ [†] Pap Smear at Selected Sites
Specimens for Storage	Vaginal Swabs Cervicovaginal Lavage (Month 3 only) Plasma PBMC (Week 2 and Month 3 only)

*If indicated; [†]PAP smears should be done at 6 month intervals in the first year after seroconversion, and then annually if the initial tests are negative.

Table 5: Month 6 and Q6 Months Visits After Initiation of ART

Month 6 and Q6 Months Visits After Initiation of ART	
Component	Procedure/Analysis
Administrative Procedures	Update Locator Information Schedule Next Visit Reimbursement
Clinical Assessments	Update Medical History Update Clinical Events Concomitant Medications Assessment Antiretroviral Treatment Record Targeted Physical Exam Gynecologic Exam *Provide Test Results *Treatment or Referral
Behavioral Assessments	Follow-up Behavioral Questionnaire (Month 12 and Month 24 only) If ART is begun more than 24 months after identification of seroconversion, then the Follow-up Behavioral Questionnaire is omitted at post-ART visits. Adherence Questionnaire Social Harms Assessment STI Risk Reduction and Contraception Counseling HIV-1 Secondary Prevention Counseling Provision of Condoms
Urine	*Qualitative hCG **SDA for Chlamydia and Gonorrhea (annually)
Blood	Plasma HIV-1 RNA CD4+ T-Cell Count Complete Blood Count Liver and Renal Function Tests **Syphilis Serology (annually) *HIV-1 Genotypic Resistance Test (at NL)
Pelvic Samples	**Vaginal pH **Wet Mount for BV, Candida and Trichomonas † Pap Smear at Selected Sites
Specimens for Storage	Vaginal Swabs Cervicovaginal Lavage Plasma PBMC

*If indicated; **Urine SDA for Chlamydia and Gonorrhea, Syphilis Serology, Vaginal pH, and Wet Mount should be performed at visits annually, with performance of these measures at other scheduled visits as clinically indicated; †PAP smears should be done at 6 month intervals in the first year after seroconversion, and then annually if the initial tests are negative.

7.2.3. Final Visit – All Participants

The table below lists procedures that will be conducted at the final study visit for all participants.

Table 6: Final Visit

Final Visit	
Component	Procedure/Analysis
Administrative	Update Locator Information Reimbursement
Clinical	Update Medical History Update Clinical Events Concomitant Medications Assessment *Antiretroviral Treatment Record Targeted Physical Exam Gynecologic Exam *Provide Test Results *Treatment or Referral
Behavioral	*Adherence Questionnaire Social Harms Assessment HIV-1 Secondary Prevention Counseling STI Risk Reduction and Contraception Counseling Provision of Condoms
Urine	Qualitative hCG SDA for Chlamydia and Gonorrhea
Blood	Plasma HIV-1 RNA CD4+ T-Cell Count Complete Blood Count Liver and Renal Function Tests Syphilis Serology
Pelvic Samples	Vaginal pH Wet Mount for BV, Candida and Trichomonas */† Pap Smear at Selected Sites
Specimens for Storage	Vaginal Swabs Cervicovaginal Lavage Plasma PBMC

*If indicated; †PAP smears should be done at 6 month intervals in the first year after seroconversion, and then annually if the initial tests are negative.

MTN-015 participants will be asked to attend a final study visit prior to their termination of participation in the study. This visit will be similar to other follow-up visits.

7.3. Interim Visits

Interim visits may be performed at any time during follow-up. Possible reasons for interim visits include:

- Administrative reasons, e.g., a participant may have questions for study staff or need to re-schedule a follow-up visit
- Clinical reasons, e.g., to report new symptoms or clinical events, or to report initiation of ART
- Psychosocial reasons, e.g., to request HIV-1-related or other counseling or referrals

All interim visits will be documented in participants' study records and when needed, on applicable case report forms.

7.4. Behavioral Evaluations

Behavioral evaluations will include the Baseline Behavioral Questionnaire and a Follow-up Behavioral Questionnaire. These questionnaires will capture participant responses related to sexual behaviors and partnership status. For participants who do not report past or current use of ART at enrollment, behavioral questionnaires will not include questions on ART adherence, and will be performed at 3, 12, and 24 months post-seroconversion. For participants on ART, behavioral questionnaires will be performed at 3, 12, and 24 months post-initiation of ART and an adherence questionnaire will be completed at Month 3, Month 6, and every 6 months thereafter. All behavioral evaluations, as well as the Social Harms Assessment, will be available in the MTN-015 Study-Specific Procedures Manual at www.mtnstopshiv.org.

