10.2.2. Secondary Endpoints

Consistent with the secondary study objectives, the following secondary endpoints will be assessed:

- **Immunologic response. (CD4+ T cell count).** CD4⁺ T cell counts at Weeks 0 and 2, Months 1, 3, 6 and every 6 months thereafter. Time from seroconversion to immunologic failure will be compared between active microbicide and placebo/control groups. Immunologic failure is defined as two consecutive measurements of CD4+ T-cell count within or below the range of 200-250 cells/mm³, or the development of an AIDS defining illness.
- **Virologic and immunologic responses (CD4+ T-cell count) after initiation of ART.** CD4+ T-cell count and blood plasma HIV-1 RNA levels over time after initiation of ART. Time from initiation of ART to immunologic and virologic failure.
- **HIV-1 related and AIDS-defining events.** Occurrence and frequency of HIV-1 related and AIDS-defining events. Time from enrollment to time of first AIDS-defining event or death.
- **Sexual behavior, partnership status, and occurrence of social harms.** Sexual behavior over time following seroconversion at Months 0, 3, 12, and 24 months. Participants who enroll ≥3 months after seroconversion will be followed at 12 months and 24 months only.
- **HIV-1 genotypic mutations and drug resistant virus.** Prevalence of HIV-1 genotypic mutations over time and drug resistant HIV-1 virus in plasma and genital tract. Proportions of infected participants acquiring a drug resistant HIV-1 virus.

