Many other secondary analyses will be performed using the secondary endpoints described in Section 10.2.2. Time-to-event secondary endpoints will be analyzed according to the Kaplan-Meier method where differences between groups will be tested using the stratified log-rank test while secondary endpoints involving repeated assessment over time (e.g. sexual behavior) will be compared at selected time points. At each of the selected time points, comparison of the two groups will be made using Fisher exact test or Wilcoxon rank-sum test as appropriate. More generally, GEE (Generalized Estimating Equation) methods and robust variance estimates will be used to evaluate group.

Data on behaviors that are associated with HIV-1 transmission such as sexual intercourse without a condom, the frequency of sexual intercourse, and the numbers of sexual partners will be measured over time among women in this study and compared to the same behaviors reported by women in ongoing microbicide trials (including parent trials) who are HIV-1 negative and to large household surveys of women (Demographic Health Surveys) in the same countries as the women in this study are located.

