APPENDIX I: SCHEDULE OF STUDY VISITS AND EVALUATIONS

	Screening and Enrollment	Month 1 Post-Seroconversion	Month 3 Post-Seroconversion	Mo. 6/Q6 Mo. Post-Seroconversion	Week 2, Month 1, Month 3 Post-ART Initiation	Month 6 and Q6 Months Visits After Initiation of ART	Final Visit
Administrative Procedures							
Informed Consent	X						
Review Parent Study Records (Confirm HIV-1 Seroconversion)	X						
Eligibility Determination	X						
Assign Participant ID	X						
Update Locator Information	X	X	X	X	X	X	X
Update Demographics	X						
Schedule Next Visit	X	X	X	X	X	X	
Reimbursement	X	X	X	X	X	X	X
Clinical							
Record/Update Medical History and Clinical Events	X	X	X	X	X	X	X
Acute Seroconversion Assessment	X						
Concomitant Medications Assessment	X	X	X	X	X	X	X
Antiretroviral Treatment Record	▲				X	X	▲
Provide Test Results	▲	▲	▲	▲	▲	▲	▲
Treatment or Referral	▲	▲	▲	▲	▲	▲	▲
Complete Physical Exam	X						
Targeted Physical Exam		X	X	X	X	X	X
Gynecologic Exam	X	X	X	X	X	X	X
Behavioral							
Baseline Behavioral Questionnaire	X						
Follow-Up Behavioral Questionnaire			X	X (Mo. 12 and Mo. 24)	*X (Mo. 3 Post-ART Initiation)	*X (Mo. 12 and Mo. 24 Post-ART Initiation)	
Adherence Questionnaire	▲				X Mo 3	X	▲
STI Risk Reduction/Contraception Counseling	X			X		X	X
HIV-1 Secondary Prevention Counseling	X			X		X	X
Social Harms Assessment			X	X	X	X	X
Provision of Condoms	X	X	X	X	X	X	X
Laboratory Procedures							
Approx. Total Blood Volume Collected (mL)	83	72	77	77	72	77	77
Urine Qualitative hCG	X	▲	▲	▲	▲	▲	X
Urine SDA for Chlamydia, GC	X	▲	▲	▲ (Annual)	▲	▲ (Annual)	X
CBC, Liver and Renal Function	X		X	X	▲	X	X
Syphilis Serology	X	▲	▲	▲ (Annual)	▲	▲ (Annual)	X
CD4+ T-Cell Count	X	X	X	X	X	X	X
Plasma HIV-1 RNA	X	X	X	X	X	X	X
HIV-1 Genotypic Resistance Test (at NL)	X				▲	▲	
HIV ELISA and Western Blot	▲						
HSV-2 Serology (using archived plasma)	X						
Vaginal pH	X	▲	▲	▲ (Annual)	▲	▲ (Annual)	X
Wet Mount for BV, Candida, Trichomonas	X	▲	▲	▲ (Annual)	▲	▲ (Annual)	X
PAP Smear at Selected Sites	X	▲	▲	▲ (Annual)	▲	▲ (Annual)	▲
Specimens for Storage							
Vaginal Swabs	X	X	X	X	X	X	X
Cervicovaginal Lavage	X	X	X	X	X (Mo. 3)	X	X
Plasma	X	X	X	X	X	X	X
Serum	X						
PBMC	X	X	X	X	X (Wk. 2 and Mo. 3)	X	X

X=protocol-defined procedure; ▲=performed as indicated; *If ART is begun more than 24 months after identification of seroconversion, then the Follow-Up Behavioral Questionnaire is omitted at post-ART visits.

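### Once a woman starts ART, her behavioural questionnaire moves to the ART clock, and nothing preserves the Month 12 and Month 24 post-seroconversion assessments that the secondary endpoint requires

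*Protocol*

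**What the plan says.** Protocol section 10.2.2 defines the endpoint as "Sexual behavior over time following seroconversion at Months 0, 3, 12, and 24 months". For late enrollers it adds: "Participants who enroll ≥3 months after seroconversion will be followed at 12 months and 24 months only". Section 10.6.2 says that "secondary endpoints involving repeated assessment over time (e.g. sexual behavior) will be compared at selected time points", and then mentions GEE methods more generally.

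The schedule follows two clocks. Under section 7.2, women who start ART during follow-up begin on the seroconversion schedule "and then switch to the schedule in Section 7.2.2 after initiation of ART use". Section 7.2.1 confirms the replacement: "For participants who have initiated ART prior to these visits, procedures specified in Tables 4 and 5 will be followed". Tables 4 and 5 and Appendix I place the Follow-up Behavioral Questionnaire at Months 3, 12 and 24 after ART initiation, and section 7.4 says the same: "For participants on ART, behavioral questionnaires will be performed at 3, 12, and 24 months post-initiation of ART". There is one exception: "If ART is begun more than 24 months after identification of seroconversion, then the Follow-Up Behavioral Questionnaire is omitted at post-ART visits".

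The preceding sentence of section 7.4 defines the other group by ART use at enrollment: "For participants who do not report past or current use of ART at enrollment, behavioral questionnaires will not include questions on ART adherence". It gives that group questionnaires at 3, 12 and 24 months post-seroconversion. A woman who enrolls off ART and starts it later fits both descriptions.

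**The concern.** The endpoint and the data collection run on different clocks for any woman who starts ART within 24 months of seroconversion. The objective is to describe change after seroconversion, and no endpoint in section 10.2.2 times sexual behaviour from ART start. A woman who starts ART at Month 5 has target dates at Months 3, 8, 17 and 29 after seroconversion, and none of these lies in the Month 12 or Month 24 window. Neither the Final Visit (Table 6) nor the interim visits (section 7.3) schedule a follow-up behavioural questionnaire that would fill the gap.

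An answer never collected near Month 12 or 24 cannot be recovered in the analysis. Whether it is collected depends on ART status and on the date ART began, so the schedule itself creates the missing data. Women who enroll three or more months after seroconversion have most to lose, because Months 12 and 24 are their only planned follow-up points for this endpoint.

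**Working it through.** **Inputs**
- Endpoint times: Months 3, 12 and 24 after seroconversion (section 10.2.2).
- Questionnaires before ART: Months 3, 12 and 24 after seroconversion (Tables 2 and 3).
- Questionnaires after ART starts at month *s* (*s* up to 24): *s*+3, *s*+12 and *s*+24 (section 7.4, Tables 4 and 5, Appendix I).
- Windows: midpoint to midpoint on both schedules (section 7.2).
- ART uptake: under 10% in the first 6-12 months (section 10.3).

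**Step 1: reproduce the stated window.** For Month 24, (18+24)/2 = 21 and (24+30)/2 = 27, as section 7.2 states. For Month 12, (6+12)/2 = 9 and (12+18)/2 = 15.

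**Step 2: gaps when ART visits fall on target dates.** The woman is taken to be enrolled before the window in question.

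Month 12 window, 9-15:
- *s*+12 falls inside when *s* ≤ 3.
- *s*+3 falls inside when 6 ≤ *s* ≤ 12.
- If *s* > 12, the pre-ART Month 12 questionnaire has already been given.
- Gap: 3 < *s* < 6.

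Month 24 window, 21-27:
- *s*+24 falls inside when *s* ≤ 3.
- *s*+12 falls inside when 9 ≤ *s* ≤ 15.
- *s*+3 falls inside when 18 ≤ *s* ≤ 24.
- Gaps: 3 < *s* < 9 and 15 < *s* < 18.

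**Step 3: effect of the ART visit windows.** By the same midpoint rule, the three ART-clock questionnaires may be given at *s*+2 to *s*+4.5, *s*+9 to *s*+15 and *s*+21 to *s*+27. For *s* = 5 these are Months 7-9.5, 14-20 and 26-32. They overlap the Month 12 window at 9-9.5 and 14-15, and the Month 24 window at 26-27. A sufficiently early or late visit could therefore close the gap. In this example the Month 12 gap closes only if the ART Month 3 visit is at least 1 month late or the ART Month 12 visit at least 2 months early. The Month 24 gap closes only if the ART Month 24 visit is at least 2 months early. Off-target visits could also open gaps elsewhere.

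**Step 4: share of starters.** The protocol gives no distribution of start times, so uniform starts are assumed, with visits on target.

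| Starts uniform over | Miss Month 12 | Miss Month 24 |
|---|---|---|
| Months 0-12 | 3/12 = 25% | 6/12 = 50% |
| Months 0-24 | 3/24 = 12.5% | 9/24 = 37.5% |

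**Step 5: number of women.** Section 10.3 implies 172 × 0.85 = 146.2 enrolled and 146.2 × 0.95 = 138.9 at one year (138 stated). Ten percent is about 14 to 15 early starters.
- Missing Month 12: 0.25 × 14 to 15, about 4 women.
- Missing Month 24: 0.50 × 14 to 15, about 7 women.

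The timing assumption matters. If every early start fell in Months 0-3, the count would be zero. If every one fell in Months 3-6, all 14 to 15 would miss both windows.

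**Step 6: is a visit already there?** For starts in Months 3-6, the ART Month 6 visit falls at 9-12. For starts in Months 3-9, the ART Month 18 visit falls at 21-27. For starts in Months 15-18, the ART Month 6 visit falls at 21-24. Every gap contains a scheduled visit.

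**The case against.** The two clocks are deliberate. Sections 4.1 and 7.2 set them out, and the rule dropping the questionnaire for starts after Month 24 shows that their interaction was considered. The behavioural objective is descriptive and one of many secondary objectives. Section 10.6.2 does not name its time points and allows GEE, and details of that kind are commonly left to an analysis plan. All of this stands and limits the severity. It does not remove the conflict: section 10.2.2 does name Months 12 and 24 after seroconversion, and GEE on actual dates can use off-window answers without supplying those that were never collected.

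A reader might infer several stronger claims that the document does not support:
- **The protocol's windows guarantee that these questionnaires are lost.** They do not. The gaps hold on target dates, and the ART windows overlap the seroconversion windows.
- **Many women are affected.** The percentages are shares of ART starters, and the protocol expects few early ones.
- **Starters are sicker or pregnant, so the results are biased in a known way.** No text says that starters' behaviour differs, and section 4.1 does not count single-dose nevirapine for PMTCT as ART initiation. The missingness depends on ART status, but the direction and size of any bias are unknown.
- **Section 7.4 alone replaces the seroconversion schedule.** It is ambiguous for women who start ART after enrollment. The replacement comes from sections 7.2 and 7.2.1.

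**Conclusion.** The concern holds as a conflict between the schedule and a stated secondary endpoint, of minor to moderate severity. The primary endpoint, plasma HIV-1 RNA at 12 months, is unaffected. The expected loss among early starters is about 4 women at Month 12 and 7 at Month 24, out of roughly 140. That estimate rests on uniform start times, on-target visits and the protocol's 10% ceiling. Losses among women starting in Months 12-24 come on top and cannot be sized, because the protocol gives no figure for them. The cohort could also grow towards the approximate 500 in the Protocol Summary.

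**What to change.** In section 7.4, Tables 4 and 5 and Appendix I, require the Follow-up Behavioral Questionnaire at the already scheduled visit closest to Months 12 and 24 after seroconversion for every woman, regardless of ART status. Keep the ART-clock questionnaires as additional assessments. Reword section 7.4 so that women who start ART during follow-up are covered explicitly, rather than grouping women by ART use at enrollment in one sentence and by being on ART in the next.

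The cost is at most two extra questionnaires per ART starter, and none where an ART-clock questionnaire already falls at the chosen visit. No new visits are needed. The alternative is to redefine the endpoint in section 10.2.2 for ART starters. That would also reconcile the text, but starters would no longer be observed at the same times after seroconversion as other women.
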